The sensitivity of each RT-PCR equipment and kit used varies in the number of CTs to generate the qualitative result (Positive or negative)¹¹.

So, to extract RELIABLE **QUANTITATIVE** data, both the equipment and the reagent kit must be standardized to avoid discrepancies. However, this is not enough, so a standard curve should provide the correlation between CTs and *viral RNA copy* number.

Therefore, we will use the QuantStudio5 RT-PCR equipment, *Applied Biosystems*, NS: 272525086, ANVISA Reg.: 10358940069, to issue reports for statistical accounting and to assist in the standard curve analysis, via dedicated software¹². We will also use the TaqPathTMCOVID-19 CE-IVD RT-PCR¹³ kit (ANVISA Reg.: 10358940107), which can provide us with the viral load-related CT values (viral RNA copies) as a function of the standard curve constructed with the positive control (TaqPath COVID-19 *Control*), which is SARS-CoV-2 viral RNA at a known concentration of 1 x 104 copies/ μ L. By means of the standard curve, using serial dilutions of the positive control, we can arrive at the

concentration (in number of copies) of the viral RNA present in each sample from the volunteers and participants.

For example, it is common to determine the concentration of proteins in a sample using a colorimetric method, the Bradford assay. Similarly, by performing serial dilutions of the positive control we can establish a standard curve (equation y = ax + b) using the CTs obtained for each point on the concentration curve.

The positive RT-PCR result occurs at CTs ≤37. In this case, when viral RNA is present, the specific probe used for detection of SARS-CoV-2 is broken by DNA polymerase, emitting fluorescence. The higher the viral RNA copy number, the higher the fluorescence and therefore the CT value appears earlier during the reaction.

The lower the copy number of the viral RNA, the lower the fluorescence and, consequently, the CT value appears later. CTs values >37 are considered negative. By establishing a curve of viral RNA concentration (present in the positive control), we will obtain a curve of CTs, from lower values (higher viral RNA copies) to higher values (lower viral RNA copies).

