11.3. METHOD OF STATISTICAL ANALYSIS

All statistical tests will be two-sided tests.

- If the p-value is ≤0.05, it is considered that there is statistical significance in the test (unless otherwise specified).
- The quantitative indices describe the mean value, standard deviation, median, minimum value, maximum value, lower quartile (Q1), upper quartile (Q3) to be calculated, and the rank indices describe the frequency and percentage of cases.
- Comparison of the two groups under general conditions will be analyzed with appropriate methods according to the types of indicators. Student's ttest or Mann-Whitney test will be used to compare the groups for quantitative data. Chi-square test or Fisher's exact test will be used for categorical data.
- The selected cases should be grouped and at the end of the study determine the three analysis data sets (FAS, PPS, SS).
- For the analysis of demographic information and baseline eigenvalues, the mean value, standard deviation, quartiles, minimum value and maximum value should be calculated for numeric variables. For categorical data, frequency and percentage will be calculated.
- For analysis of medication and drug combination adherence one should calculate the percentage of individuals whose medication adherence is at

least 80-100%. An analysis of the classification of the combination of drugs should also be done.

• For analysis of the primary effectiveness indicator:

Primary Goal

To evaluate the **efficacy and safety of** AZVUDINE (FNC) versus placebo in patients infected with moderate to severe stage SARS-COV-2;

Analysis method:

For the efficacy analysis a logistic regression model will be used with the dependent variable "The proportion of participants with clinical improvement [Period: until D15, approximately 14 days]" and independent variables allocation group, AZVUDINE (FNC) or PLACEBO. For the Safety analysis a logistic regression model will be used with the dependent variable "occurrence of serious adverse events" and independent variables allocation group, AZVUDINE (FNC) or PLACEBO. As a support analysis, with exploratory character, both for efficacy and safety, covariate models will be built as well as other variables that present, in the univariate analysis, statistical significance.

Secondary objective

To evaluate the **clinical outcome** between the AZVUDINE (FNC) group versus placebo in patients infected with moderate to severe stage SARS-COV-2;

Analysis method:

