Univariate analysis of the clinical outcome variables and with the group variable.

- For the secondary efficacy indicator analysis, the coronavirus viral load changes compared to baseline should be calculated for the experimental and control groups separately, as well as the value of the difference between the viral load changes compared to baseline for both groups. The ANCOVA model will be used to estimate the impact of treatment on viral load changes adjusting for other study variables such as disease severity, age, weight, and comorbidities, etc.
 - For analysis of the secondary efficacy indicator one should stratify according to the severity of the disease (severe, severe), following the following statistical methods:

PRIMARY ENDPOINT			ANALYSIS METHOD
•	Propo	rtion of participants with clinical status	Teste t de
	impro	vement [Period: until D15,	Student/Teste de
	appro	ximately 14 days].	Mann-Whitney
	0	The criterion for a participant to have	
		an improvement in clinical status is a	
		decrease on the WHO Clinical	
		Improvement Ordinal Scale in at least	
		one category compared to screening	
		(WHO, Jun/2020).	

SEC	CONDARY OUTCOMES	
•	Proportion of participants with a clinical	Pearson's Chi-
	outcome of cure during the study; [Period:	square test
	until D15, D21, and D28, approximately 14-	
	30 days].	

;	inic	al Trial Design	
		o The clinical endpoint of cure is	Student's t-test /
		defined in this protocol as the	Mann-Whitney
		absence of viral RNA in	test
		collected samples and clinical	
		conditions for	
		hospital discharge.	
	•	Time to normalization of body temperature	Student's t-test /
		(below 37.6c, axillary); [Period: until D15,	Mann-Whitney
		D21 and D28, approximately 14-30 days].	test
		Time to improvement of diarrhea,	Student's t-test /
		myalgia, fatigue, malaise, cough and	Mann-Whitney
		headache; [Period: until D15, D21 and	test
		D28, approximately 14-30 days].	
		Changes in liver and kidney function	Student's t-test /
		baselines, and inflammatory and	Mann-Whitney
		immunological markers: [Period: until	test
		D15, D21 and D28, approximately 14-30	
		days]	
		 Lab tests performed on days D1, 	
		D3, D5, D7, D9, D13, D15, D21,	
		D28, and D60.	
		Evaluation of the time to negative	Student's t-test /
		conversion of SARS-CoV-2 viral load by	Mann-Whitney
		RT-PCR between AZVUDINE (FNC) group	test
		and placebo- control group; [Period: until	
		D15, D21 and D28, approximately 14-30	
		days].	

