- Evaluation of the number of cycles for the detection of SARS-CoV-2 viral load byRT-PCR and application of the standard curve for viral load calculation; [Period: until D15, D21 and D28, approximately 14-30 days].
- Student's t-test /
 Mann-Whitney
 test
- Analysis of the relationship between the calculated viral load and the clinical outcome of participants in the AZVUDINE (FNC) group versus the placebo control group; [Period: until D15, D21 and D28,

Generalized linearregression model

- approximately 14-30 days].
- Time and proportion of lung imaging improvement during treatment (Pattern of ground-glass opacities, mosaic paving, alveolar consolidation, reticular pattern/septal thickening, opacity with inverted halo, pleural/pericardial effusion, fibrosis and/or lymphadenomegaly); [Period: until D15, D21 and D28, approximately 14-30 days].

Student's t-test /
Mann-Whitney test
/ Pearson's chisquare test

 Time of improvement and proportion of respiratory symptoms and signs during treatment (Lung rales, cough, sputum, sore throat); [Period: until D15, D21, and D28, approximately 14-30 days].

Student's t-test /
Mann-Whitney test
/ Pearson's chisquare test

·IIIIIC	ai Illai Desigli	
•	Time to normalization of _{O2} saturation (above 95%); [Period: until D15, D21 and D28, approximately 14-30 days].	Student's t-test / Mann-Whitney test
•	Time to normalization of respiratory rate to levels ≤ 24rpm, in room air; [Period: until D15, D21 and D28, approximately 14-30 days]	Student's t-test / Mann-Whitney test
•	Frequency of supplemental oxygenation or non-invasive ventilation; [Period: until D15, D21 and D28, approximately 14-30 days].	Student's t-test / Mann-Whitney test / Pearson's chi- square test
•	Frequency of invasive mechanical ventilation or extracorporeal membrane oxygenation (ECMO); [Period: until D15, D21 and D28, approximately 14-30 days].	Student's t-test / Mann-Whitney test
•	Proportion of moderate cases that progressed to severe cases requiring intensive care unit (ICU) care; [Period: until D15, D21, and D28, approximately 14-30 days].	Pearson's Chi- square test
•	Length of hospital stay; [Period: until D15, D21 and D28, approximately 14-30 days].	Student's t-test / Mann-Whitney test

Jinicai Triai Design	
 Occurrence of drug interactions; [Period: until D15, D21 and D28, approximately 14- 30 days]. 	Pearson's Chi- square test

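### Section 11.3 gives viral load two analyses without ranking them, and neither names baseline viral load as a covariate or states a log scale

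*Protocol*

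**What the plan says.** Section 11.3 treats viral load in two places.

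- **Text on the secondary efficacy indicator.** It asks that "the coronavirus viral load changes compared to baseline should be calculated for the experimental and control groups separately", together with the difference between the groups. It then names the model: "The ANCOVA model will be used to estimate the impact of treatment on viral load changes". Which covariates enter is given only by example, and the model is described as "adjusting for other study variables such as disease severity, age, weight, and comorbidities, etc".
- **Table of methods.** The next sub-item introduces the table: "For analysis of the secondary efficacy indicator one should stratify according to the severity of the disease (severe, severe". Both strata carry the same label. The table row reads "Evaluation of the number of cycles for the detection of SARS-CoV-2 viral load byRT-PCR and application of the standard curve for viral load calculation", and the method beside it is Student's t-test / Mann-Whitney test. This matches the section's general rule: "Student's ttest or Mann-Whitney test will be used to compare the groups for quantitative data".

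Section 5.3.2 explains how load is obtained. Ct values from serial dilutions of a positive control give a line ("we can establish a standard curve (equation y = ax + b) using the CTs obtained for each point on the concentration curve"), from which each sample's concentration is read as a number of copies. A Ct above 37 counts as negative. Table 10 schedules RT-PCR both at screening (D-1) and on D1.

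**The concern.** An adjusted model of change and an unadjusted two-group comparison are different analyses and can give different estimates and p-values. The slash in the table adds a further choice between a mean-based and a rank-based test. Whoever writes the detailed analysis must depart from one of the two protocol statements or rank them without guidance.

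Two features of viral load make the choice matter. First, change from baseline is usually strongly related to the baseline value. Leaving that value out costs precision and carries any chance baseline imbalance into the estimate. Second, loads span orders of magnitude. If change is computed in raw copies, its mean reflects the few participants who started very high. Section 5.3.2 sets up a quantification process specifically to relate load to treatment and clinical course, so an insensitive analysis would waste data that the trial collects at some effort.

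**Working it through.** **Plan's own figure.** The protocol gives no precision or power figure for viral load. The nearest stated number is the 81 evaluable per group for the primary endpoint (section 11.1). From its inputs, n = (1.645 + 0.842)² × [0.667 × 0.333 + 0.281 × 0.719] / (0.386 − 0.205)² = 80.04, so 81 per group. This reproduces the plan with a one-sided 0.05 level. I use 81 below only as the planned evaluable number.

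**Assumed inputs.** The protocol gives neither the standard deviation of viral load nor the correlation r between baseline and follow-up, so r is taken over a range.

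**Precision.** Let σ² be the variance at follow-up.

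- Unadjusted change score, with the same variance at both times: 2σ²(1 − r).
- Unadjusted follow-up value: σ².
- ANCOVA with baseline as covariate: σ²(1 − r²).

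The ratio of ANCOVA to change score is (1 − r²) / [2(1 − r)] = (1 + r)/2. The ratio of ANCOVA to follow-up value is 1 − r².

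| r (assumed) | Against change score | Reduction | 81 per arm worth | Against follow-up value | Reduction |
|---|---|---|---|---|---|
| 0.3 | 0.65 | 35% | 81/0.65 ≈ 125 | 1 − 0.09 = 0.91 | 9% |
| 0.5 | 0.75 | 25% | 81/0.75 = 108 | 1 − 0.25 = 0.75 | 25% |
| 0.7 | 0.85 | 15% | 81/0.85 ≈ 95 | 1 − 0.49 = 0.51 | 49% |

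The fourth column is the number per arm that an unadjusted change score would need to match 81 per arm analysed with baseline adjustment. At r = 0.9 the gain over a change score is only 5%. The two comparisons move in opposite directions as r rises, so the size of the gain depends on what the table row means. Its sign does not: baseline adjustment is more precise than either at every r in the table.

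The gain over the ANCOVA with severity, age, weight and comorbidities cannot be worked out. It depends on how much of the baseline load those covariates already explain, and the protocol has no figure for that.

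**Scale.** Section 5.3.2 cites a study with Ct of 18–22 in critically ill and 32–38 in mild patients. The gap is 32 − 22 = 10 to 38 − 18 = 20 cycles. Assuming one doubling per cycle, that is 2¹⁰ ≈ 1,000-fold to 2²⁰ ≈ 1,000,000-fold in copies.

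A simulation shows what this could do. It used 600 runs per scenario and 81 per arm. Loads were log-normal with a log10 SD of 1.0 to 2.0 and r of 0.3 to 0.7. Mean log10 load fell from 5 to 3 in the control arm, and the true effect was 0.45 SD on the log10 scale. No detection limit was applied, and tests were two-sided at 0.05.

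| Analysis | Power |
|---|---|
| Change in raw copies, t-test | about 0–3% |
| Change in raw copies, Mann-Whitney | 4–11% |
| Change in log10, t-test | 68–96% |
| log10 ANCOVA with baseline | 84–98% |

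Under these assumptions a raw-copy change is almost entirely the baseline load with its sign reversed, so it says little about treatment. The figures illustrate the scale problem and do not predict this trial's power.

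**The case against.** The strongest reply is that much of this belongs in a statistical analysis plan, and that the protocol is less contradictory than it looks.

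- **Baseline is not excluded.** The covariate list is illustrative and open-ended. This stands: baseline viral load is unnamed, not ruled out.
- **The table row does not mention change.** It covers cycle number and calculated load, so it may concern a different quantity from the ANCOVA. An unadjusted test beside an adjusted model is also a familiar pattern, and section 11.3 uses it for the primary endpoint, where it labels the covariate models as supportive. This stands in part. For viral load no such label is given, and the text sends the same secondary efficacy indicator to both methods.
- **The table's tests are not simply unadjusted.** It is introduced with stratification by severity. That is true, but the two strata named are identical, and a t-test or Mann-Whitney test as written does not say how strata are combined.
- **Raw copies may never be averaged.** Ct is already logarithmic. For load values, though not for change scores, a Mann-Whitney test is unaffected by taking logs. This stands, so the scale point is conditional.

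A reader might also infer that the analyst is free to choose the method after seeing group results. The document does not support that: section 5.4.4 places disclosure of the groups after the final statistical plan, the audit report and database lock. Nor does it support treating 35%, 25% and 15% as the plan's actual loss. Those figures take an unadjusted change score as comparator, while the change analysis the plan names is a covariate-adjusted ANCOVA.

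**Conclusion.** The point holds in a limited form. Section 11.3 gives viral load two methods and ranks neither. The named covariates of the adjusted one leave out baseline viral load, and no scale is fixed for a quantity calculated in copies.

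With assumed r of 0.3 to 0.7, baseline adjustment would reduce variance by 35% to 15% against an unadjusted change score (equal variances at both times assumed), or by 9% to 49% against an unadjusted follow-up value. The gain over the listed-covariate ANCOVA is unknown. If raw-copy change were analysed, scale would matter more than the covariate, but the protocol does not say that it will be.

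Viral load is one of many secondary outcomes, and the primary endpoint and its analysis are untouched. This is an improvement worth making at almost no cost, not a threat to the trial's main conclusion.

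**What to change.** In section 11.3, name one main analysis of viral load: ANCOVA of log10 viral load (or Ct) at a stated visit, with treatment, baseline log10 viral load (or Ct) and severity as covariates. In the same place:

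- say whether the D-1 or the D1 sample is the baseline;
- say what value a sample with Ct above 37 receives;
- label the t-test / Mann-Whitney row as supportive;
- correct the duplicated severity label.

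The cost is a few sentences. RT-PCR is already scheduled at both D-1 and D1, so no extra sample, visit or participant is needed.

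Because section 5.4.4 requires the final statistical plan before group disclosure, the change should be settled before that step.

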2.5. CLINICAL STUDIES WITH COVID-19

FNC-Hope1 was a randomized, open-label, controlled clinical trial to evaluate the safety and efficacy of AZVUDINE tablets in the treatment of COVID-19, conducted at *People's Hospital of Guangshan County*, China.

Twenty individuals with COVID-19 with mild to moderate symptoms were randomly and equally assigned to 2 groups, experimental and control. Subjects who received conventional treatment with FNC + (no antiviral drugs) after diagnosis **reduced** the time to become nucleic acid negative for the first time by -7.3 days, compared to those who received conventional treatment alone (9.8). Subjects who received conventional treatment + FNC (no antiviral drugs) reduced the time to nucleic acid

negative for the first time by -6.8 days compared to those who received conventional treatment alone (11,30).

[figure not shown]

Figure 3: Kaplan-Meier curves of two consecutive negative tests for SARS-CoV-2 (a) first and b) second) in FNC and control group. Data are percent (%). Differences between groups were using the Log-rank test (Mantel-Cox)

On the fourth day after treatment, the rate of the first negative nucleic acid conversion reached 100% in patients in the FNC group and 30% in patients in the control group. Kaplan-Meier curves indicate the significant difference (p = 0.0013). On day 6, the negative conversion rate of the second nucleic acid reached 100% in patients of the FNC group and 40% in patients of the control group. Kaplan-Meier curves indicate the significant difference (p = 0.0011).

Regarding the safety analysis, there was no adverse event in the experimental group and three adverse events in the control group with an incidence of 30% (3/10) during the study period. All adverse events were grade 2 and were followed up until they disappeared. There were no serious adverse events, serious adverse reactions, major adverse events, or death events during the study period. The demographics and baseline characteristics of the subjects were similar and the proportions between the 2 groups were relatively balanced and comparable.

In 3 other hospitals in China, during the periods February 14 to March 10, March 1 to March 22, and March 7 to March 30, 32 volunteers with mild to severe symptoms were treated with different antiviral therapeutic approaches, including Arbidol,

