VISIT 3-16: PROCEDURE (D1-D14)

The treatment period will start on D1 according to randomization.

The treatment will last up to 14 days, and may be stopped early in case of treatment success (2 consecutive negative RT-PCR tests), participant dropout, or at the Principal Investigator's option, if deemed necessary for the safety of the participant.

For the **Early Termination (ETA)** of treatment, participants should follow the routine from visit 17: End of Treatment (D15), in advance.

The Principal Investigator for the study will be available to answer any questions.

The experimental drug should be administered daily at 8 pm to minimize the risk of falling, since in preliminary studies, it was observed that vertigo (incidence ≥5%) appears to be an AE likely related to FNC. However, no restrictions on meals.

The following procedures will be performed in the V3-16 visits:

- Administration AZVUDINE or PLACEBO daily, at the same time at 8pm, to minimize the risk of falling, since in preliminary studies, it was observed that vertigo (incidence ≥5%) may be an AE likely related to FNC;
- Monitoring drug interactions and AEs on a daily basis;
- Monitoring symptoms, vital signs, oximetry and blood glucose daily;
- Collection of blood samples and respiratory sample (nasal and oropharyngeal swab) for safety and efficacy monitoring tests every 48h);
- CT scan of the lung every 4 days and electrocardiogram on days D1 and D11;

The Principal Investigator may adjust the procedures performed during treatment according to the condition of the research participant and the results of clinical examinations.

VISIT 17: END OF TREATMENT (D15)

At the end of treatment or discontinuation of the investigational drug or PLACEBO, all participants will be required to undergo procedures and tests for safety and efficacy monitoring. The procedures should be performed before discharge from the hospital approximately 24 hours after the administration of the last dose of the investigational drug or PLACEBO, because for the 5 mg dose of AZVUDINE, the mean half- life is 13.8 hours, and it is excreted in the urine within 24 hours.

The treatment will last up to 14 days, and may be stopped early in case of

treatment success (2 consecutive negative RT-PCR tests), participant dropout, or at the Principal Investigator's option, if deemed necessary for the safety of the participant.

The following procedures will be performed at the V17 visit:

- Monitoring drug interactions and AEs;

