- Symptom monitoring, vital signs, oxygen and blood glucose measurement;
- Collection of blood samples and respiratory sample (nasal and oropharyngeal
- swab) for safety and efficacy monitoring tests;
- CT scan of the lung and electrocardiogram.
- Collecting blood for a pregnancy test (women of childbearing age).

VISIT 18: FOLLOW-UP (D21)

Participants who, even after the end of treatment, remain in the hospital must undergo the procedures and tests for safety and efficacy monitoring that are scheduled to occur approximately 7 days after the administration of the last dose of the investigational drug or PLACEBO.

The following procedures will be performed at the V18 visit:

- Monitoring drug interactions and AEs;
- Symptom monitoring, vital signs, oxygen and blood glucose measurement;
- Collection of blood samples and respiratory sample (nasal and oropharyngeal
- swab) for safety and efficacy monitoring tests;
- CT scan of the lung and electrocardiogram;

Participants who are not discharged from the hospital after the end of treatment will be required to follow the follow-up schedule on D28 and D60. However, safety procedures and examinations will not be exclusive to these days and research participants who still remain hospitalized will be assisted at all times by the Principal

Investigator and his team.

VISIT 19: FOLLOW-UP (D28)

Two weeks after discharge from the hospital, the volunteers will return to the research center for procedures and tests to monitor safety and efficacy after the end of treatment.

The following procedures will be performed at the V19 visit:

- Symptom monitoring, vital signs, oxygen and blood glucose measurement;
- CT scan of the lung and electrocardiogram.

The Principal Investigator may adjust the procedures performed during the hospital visit according to the condition of the research participant and the results of the clinical examinations.

VISIT 20: FOLLOW-UP (D60)

60 days after discharge from the hospital, the volunteers will return to the research center to undergo procedures and tests to monitor safety and efficacy.

The following procedures will be performed in visit V20:

- Symptom monitoring, vital signs, oxygen and blood glucose measurement.
- Collecting blood for a pregnancy test (women of childbearing age).

The Principal Investigator may order tests according to the participants' previous results.

IGZ-1

AZVUDINE Clinical Trial Design

Schedule of visits and procedures

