² The examinations and procedures under visit 17 (D15) must be performed by all participants as soon as the treatment is terminated, including participants who have stopped treatment early (AT) and for any other reason.

³ The. procedures and examinations planned to be performed at visit D28 and D60 will be determined by the Principal Investigator according to the participants' previous examinations.

⁴ For women of childbearing age only.

⁵ Visit 18 procedures will be performed only on research participants who are still hospitalized.

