8.4. AES MONITORING

If there is any abnormality or AE, serious or not, unexpected or not, during or after treatment, follow-up should be made until the clear outcome of recovery or stable status. Individuals with AEs that develop after discharge should contact the Principal Investigator or his/her team to determine what action should be taken for that individual to fully recover from the AE.

After the end of the trial, if participants have AEs again that are or could be related to the use of the investigational drug, the PI should inform the sponsor in time.

For all EAGs (including those still in the developmental stage after the end of the trial and until the end of the last patient's follow-up), the Principal Investigator should follow the patient until recovery, stabilization, or death to ensure that all

¹⁵ TGO Adult 12 to 46 U/L; TGP Adult 03 to 50 U/L (Source: Hermes Pardini Institute)

problems are resolved. Until the EAG has been resolved, the Principal Investigator should keep the sponsor informed. Detailed follow-up information should be provided, such as whether or not special treatment is needed after the trial, whether or not hospitalization is required, etc.

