 Frequency and intensity of adverse events; [Period: until D15, D21 and D28, approximately 14-30 days]. 	Student's t-test / Mann-Whitney test / Pearson's chi- square test
 Frequency and intensity of unexpected adverse events; [Period: until D15, D21 and D28, approximately 14-30 days]. 	Student's t-test / Mann-Whitney test / Pearson's chi- square test
 Frequency and intensity of serious adverse events; [Period: until D15, D21 and D28, approximately 14-30 days]. 	Student's t-test / Mann-Whitney test / Pearson's chi- square test
 All-cause mortality rate during the study; [Period: until D15, D21 and D28, approximately 14-30 days]. 	Mann-Whitnoy tost

Evaluate the tolerability of AZVUDINE (FNC)
 use at 5mg/day regimen for up to 14 days:
 [Period: until D15, approximately 14 days].

 Calculating treatment adherence;
 Total time of use of AZVUDINE
 (FNC);
 Proportion of participants who withdrew consent;
 Proportion of participants who dropped out of treatment.

Student's t-test /
Mann-Whitney test /
Pearson's chi-square test

For safety analysis, AEs should be coded according to the MedDRA terminology dictionary (version 23.0) and the following criteria should be listed and analyzed:

- o Cases of EAs, EAGs, and of EAs leading to abandonment.
- Number and the rate of "normal to abnormal" or "abnormal worsening" of the laboratory and ECG indicator after the experiment.
- Laboratory indicator, ECG, abnormal physical examination cases and clinical interpretation.

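### Adverse event frequency is compared per participant over fixed windows, but scheduled AE detection largely ends at discharge, so the arm that goes home sooner will tend to show fewer AEs

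*Protocol*

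**What the plan says.** **Analysis.** The outcome table in section 11.3 of the protocol lists "Frequency and intensity of adverse events; [Period: until D15, D21 and D28, approximately 14-30 days" and assigns it "Student's t-test / Mann-Whitney test / Pearson's chi- square test". The safety half of the primary objective is a logistic model for serious AEs with allocation group as the only independent variable. Neither analysis has a person-time denominator, an offset or censoring. Total time on drug is a separate tolerability item and is not tied to AEs.

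**Detection in hospital.** The D1-D14 visits in section 7.3 list "Monitoring drug interactions and AEs on a daily basis", with blood sampling every 48 hours. Section 5.1.1 says these samples are taken while the participant is hospitalised. For visit 17, "The procedures should be performed before discharge from the hospital approximately 24 hours after the administration of the last dose"; it is brought forward when treatment ends early. At D21, "Visit 18 procedures will be performed only on research participants who are still hospitalized".

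**Detection after discharge.** For visit 19, "Two weeks after discharge from the hospital, the volunteers will return to the research center for procedures and tests". The section 7.3 lists for visits 19 and 20 include symptom monitoring but not the AE-monitoring item that stands in the lists for visits 3 to 18. Section 8.4 says: "Individuals with AEs that develop after discharge should contact the Principal Investigator or his/her team". Against this, section 8.7 requires AE monitoring throughout the study and recording from first dose to the end of follow-up, and Table 10 shows laboratory tests and ECG at D28.

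**Link to treatment.** Section 5.1.1 ends treatment at two consecutive negative RT-PCRs and makes that result a discharge criterion. Section 6.2.4 stops dosing once the participant is no longer under hospital care.

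**The concern.** A proportion of participants with an AE by D15, D21 or D28 is comparable between arms only if an AE on any of those days is about equally likely to be found in either arm. Here the daily enquiry and the 48-hourly bloods stop at a point that depends on how quickly the participant clears virus and is discharged. If azvudine shortens that time, as sections 2.6.3 and 5.1.2 expect, participants on azvudine are searched for AEs on fewer days. Part of any apparent safety advantage would then be shorter surveillance.

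Laboratory AEs are the clearest case. Section 8.3 makes ALT and AST rises and a fall in eGFR events of special interest, and section 2.5 reports ALT and AST increases as the main adverse reactions in the Chinese phase III study. A participant at home cannot self-report these. Section 8.7 dates a laboratory AE to the day of the test, so a transient rise after discharge is either missed or dated to a later visit. At stake is the credibility of a finding of fewer, or no more, AEs on azvudine.

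**Working it through.** The protocol states no figure for AE frequency or monitored time, so there is none to reproduce. The check asks what the planned comparison shows when the true daily AE rate is the same in both arms.

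**Inputs**
- Participants: 90 per arm (section 11.1); two-sided 5% test (section 11.3).
- Scenario A, 5 v 7 monitored days: the planning medians for time to clinical improvement (section 11.1), used only as a proxy for monitored days.
- Scenario B, 4.5 v 11.3 days: RT-PCR timing in HOPE-1 (section 2.5), where azvudine shortened time to "negative for the first time by -6.8 days compared to those who received conventional treatment" alone, given as 11.30 days; 11.3 - 6.8 = 4.5.
- Daily AE rate r: an assumption, since the documents give none. Taken as 0.05, with a range of 0.03 to 0.10, equal in both arms.
- Capture c: the share of post-discharge AEs to D28 that is still recorded. Also an assumption, from 0 to 1.

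**Formula.** For monitored days t, P(at least one recorded AE) = 1 - exp(-r × [t + c × (28 - t)]).

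**No post-discharge capture (c = 0), r = 0.05**
- A: 1 - exp(-0.25) = 22.1% on azvudine; 1 - exp(-0.35) = 29.5% on placebo. Gap 7.4 points.
- B: 1 - exp(-0.225) = 20.1%; 1 - exp(-0.565) = 43.2%. Gap 23.0 points.
- With 90 per arm, a two-proportion test at nominal 5% would declare a difference in about 20% of trials (A) or 92% (B), although the rates are equal.
- Over r = 0.03 to 0.10 the gap is 5 to 11 points (A) and 16 to 32 points (B).

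**Partial capture, r = 0.05**

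| c | Gap, A (points) | Gap, B (points) |
|---|---|---|
| 0 | 7.4 | 23.0 |
| 0.25 | 4.2 | 13.4 |
| 0.50 | 2.1 | 6.9 |
| 0.75 | 0.8 | 2.7 |
| 1 | 0 | 0 |

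Example for B at c = 0.5: azvudine 4.5 + 0.5 × 23.5 = 16.25 days, giving 55.6%; placebo 11.3 + 0.5 × 16.7 = 19.65 days, giving 62.6%.

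**Blood draws.** On the D1, D3, D5... schedule, ending after about 4.5 days gives roughly 3 draws (D1, D3, end of treatment). Ending after about 11.3 days gives roughly 7 (D1 to D11, end of treatment). Scenario B would therefore mean fewer than half as many opportunities to detect a laboratory AE (3/7 = 0.43).

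**The case against.** The strongest reply is that section 8.7 already requires AE recording to the end of follow-up, that section 7.2 allows participants to be asked about AEs without limiting this to inpatients, and that Table 10 has bloods and ECG at D28. An AE that began at home on D8 can be elicited at visit 19 with its onset date. This stands in part. It rules out reading the plan as looking for AEs only in hospital, and it rules out the claim that the bias remains however completely the later visits are done: the table shows it vanishing at full capture. It does not remove the problem, because the visit lists and section 8.4 do not deliver what section 8.7 asks, and one late blood draw does not replace several 48-hourly ones.

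A reader might also infer that the bias always favours azvudine. The documents do not support that. It favours whichever arm leaves earlier; with no effect on clearance there is no differential, and with longer stays on azvudine it reverses.

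The inputs are proxies. Time to improvement is not monitored time. HOPE-1 had 20 participants with milder disease. Negative RT-PCR is only one discharge criterion, and section 9.1 also requires medical evaluation. All of this is accepted, so the percentages are illustrations.

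Finally, exposure-adjusted rates are often left to the statistical analysis plan. But section 11.3 already names per-participant tests for this outcome, and applied to the stated visit schedule those tests give a distorted contrast whenever one arm goes home earlier.

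**Conclusion.** The point holds as a defect that should be corrected: a fixed-window, per-participant AE comparison is applied to detection time that is unequal and depends on outcome. Its direction depends on which arm is discharged earlier, which the protocol expects to be azvudine.

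Its size cannot be fixed from the documents. Under equal constant risk of 0.05 per day, the spurious gap runs from 0 points (full post-discharge capture) to 7 points (5 v 7 days, no capture) or 23 points (4.5 v 11.3 days, no capture). The upper end is a total-loss scenario and should not be read as a forecast.

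The effect is likely to be strongest for laboratory AEs. A reader might infer that the primary safety result is equally exposed, but that model concerns serious AEs. Those depend less on daily bedside enquiry, are followed to resolution under section 8.4, and are sought in medical and public records under section 9.5 when contact is lost. They are probably less affected.

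**What to change.** 1. Keep the crude proportions until D15, D21 and D28, and state beside them the monitored days per arm.
2. Add a comparison of AEs and laboratory abnormalities over a common early window in which nearly all participants in both arms are still monitored daily. Choose its length blind to allocation, from pooled length of stay.
3. Add, as a supporting analysis, an AE rate per monitored day: Poisson or negative binomial with log monitored days as offset. Report post-discharge AEs separately.
4. Reconcile the visit 19-20 lists in section 7.3 and the self-contact rule in section 8.4 with section 8.7, so that the existing D28 visit includes AE enquiry with onset dates for every participant.

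Items 1 to 3 are changes of analysis wording; administration dates are already entered in the eCRF (section 6.2.4). Item 4 adds an enquiry to a visit that already takes place.

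The rate has a real downside. It assumes roughly constant risk, and monitored time is itself affected by treatment. If every participant in both arms had one AE soon after the first dose, dividing by 4.5 v 11.3 days would show 11.3/4.5 = 2.5 times the rate on azvudine from identical events. It should therefore not replace the crude and common-window comparisons. The common window in turn cannot speak to late-onset AEs.
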